The PINNACLE Registry® is the largest outpatient cardiovascular clinical data registry in the world, with millions of patients drawn from thousands of sites around the US representing over 10,000 outpatient providers. The registry has a comprehensive goal of improved patient care. In addition to using the PINNACLE Registry®, non-PINNACLE sites within large health systems will be recruited and randomized into the intervention and usual care arms respectively.

[figure not shown]
The Specific Aims of this study will be:

- To evaluate ability of ACC Solution Sets and Patient Resources to improve initiation and titration
 of GDMT for eligible patients with HFrEF Left Ventricle Ejection Fraction (LVEF) ≤ 40%.
- To evaluate change in QOL between patients in the Intervention arm and the Usual Care arm.
- Examine relative change in GDMT among higher risk versus lower risk patients in the Intervention arm and Usual Care arm.

In this randomized registry trial, sites will be invited to participate in a 6-month study aimed at various processes of care in HFrEF. Sites would be informed that they might be asked to participate in an intensive intervention to improve GDMT prescription or in a study of QOL in HFrEF. Once a list of sites interested in participating is created, sites would be randomized into two arms: an intervention group and a usual care group.

AMERICAN

(**Figure 1**): This graphic shows both usual care and intervention arm tracts.

Study Population:

- Patients from practices participating in the PINNACLE Registry® (these include those that are
 part of integrated health systems, stand-alone, and other practice environments); as well as
 patients from other practices (these include those that are part of integrated health systems,
 stand-alone, and other practice environments) with pre-existing data interfaces with study
 partner HealthReveal.
- Patient cohorts will have the following **inclusion** criteria:
 - Age ≥18 years
 - Clinical diagnosis of HF with EF ≤40% documented within 1 year of enrollment
 - Receiving ≥1 oral medication for HF at study enrollment (including diuretics, ACEI/ARB/ARNI, beta-blockers, MRA, SGLT2i or thiazide diuretics.
- Patient cohorts will have the following **exclusion** criteria:
 - Current or anticipated participation in a clinical trial
 - Currently receiving comfort care or enrolled in hospice
 - Life expectancy <1 year
 - o History of or plan for heart transplantation or left ventricular assist device

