 - Current or planned hemodialysis

The **interventional arm** will be provided tools to augment quality of care and build the patient and physician relationship through trust and shared goal-setting.

Prior to each patient appointment, on a customized *GDMT Dashboard*, the site will receive a pre-visit assessment of GDMT accompanied by recommended adjustment(s) using information extracted weekly from the sites' electronic health record (EHR). The recommended adjustment(s) will be conveyed using proprietary software from HealthReveal, with a suggested follow up plan. All reminders regarding dosing targets are based on the 2020 ACC Expert Consensus Decision Pathway for Optimization of Heart Failure Treatment.

Additionally, during visits at baseline, 3 months, and 6 months, patient-reported outcomes/QOL will be assessed.

To further facilitate optimal care, tools provided to each intervention site will include clinician and patient resources:

Information based on the 2020 ACC Expert Consensus Decision Pathway for
Optimization of Heart Failure Treatment (4). This ACC policy document sets clear goals
and provides useful logic not only for recognizing when patients were eligible for
initiation or titration of therapy, but also articulates important information for how to
achieve such titration to target. Sites randomized to the intervention will receive
distilled information from this policy document embedded into the care logic of online
decision support in the form of Reveals provided by HealthReveal in the dashboard.

 CardioSmart Heart Failure patient resources will be provided to patients via CardioSmart.org with links from patient app Medable. These resources include several patient-facing tools that serve to facilitate optimal care during the standard 20-minute visit.

Upon being diagnosed with heart failure, patients often need help "finding their new normal," which is how many people farther along in successfully managing their heart failure describe their journey. The ACC developed an action plan and accompanying tools to help patients on that journey manage their course of treatment and understand what to expect on the road to success. These tools help remind patients that they are at the center of their care and emphasize the importance of talking through and making informed decisions for managing their condition.

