- Quick Tips series provides guidance on many of the topics that are raised during medical visits, but we may not have sufficient time to go into great detail about; for example, how to record daily weights, stay active, limit sodium, take medications, watch for triggers that can exacerbate heart failure, and pay attention to emotional health and mental outlook

The Usual Care arm, will be managed as close to "true" usual care as possible. To avoid influencing management, once randomized to usual care, other than to collect QOL measures (assessed using the Kansas City Cardiomyopathy Questionnaire-23) at baseline, 3 months, and 6 months, study sites will not be contacted until the study has completed and they will be unaware of allocation to usual care. They will not receive specific pre-visit guidance, and though publicly available, sites will not be specifically provided ACC tools.

B. Data Management

Participating sites submit data using an electronic health record (EHR) system integration (SI) tool, where relevant registry data fields can be extracted from a practice's EHR and is then transmitted to a secure database.

Intervention Arm

Steps include:

Data extraction: Mapped to pre-specified data fields, a data extractor (such as that provided by FIGmd) will extract the EHR data to storage at Veradigm for PINNACLE sites. FigMD has historically provided the data extractor solution for the PINNACLE Registry and provides similar services to multiple medical societies across the United States of America. Data extracted may include the following: age, sex, LVEF, medication list (including doses), and laboratory results (such as basic metabolic panel). For the purposes of the study, data from the local EHR will be extracted on a weekly basis.

Creation of Reveals: Following, a similar extractor will then process data to HealthReveal for non-PINNACLE sites, where a dashboard will be created. This dashboard will include a) lists of eligible patients for the study and b) an update on opportunities for further medication optimization. The latter information will be based on guideline-directed medical targets as articulated in the ACC 2020 Expert Consensus Decision Pathway document on management of HFrEF. The dashboard containing the reveals will be conveyed to the sites.

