KCCQ Symptom Stability Domain: measures recent changes in patients' symptoms; their shortness of breath, fatigue or swelling. It compares patients' frequency of heart failure symptoms at the time of completing the KCCQ with their frequency 2 weeks ago. As a measure of change, it is most interpretable as a baseline assessment of the stability of patients' symptoms at the start of a study and shortly thereafter, as a measure of the acute response to treatment. This domain is not included in the summary scores.

Clinical Summary Score: includes total symptom and physical function scores to correspond with New York Heart Association ("NYHA") Classification.

Overall Summary Score: includes the total symptom, physical function, social limitations and quality of life scores.

The KCCQ-23 data will be blinded and stored until end of trial.

Following completion of usual procedures, the patient will be sent home, and followed up per study protocol at 3 month intervals for up to 3 clinical visits and with as many 'as needed' visits to achieve optimal GDMT. At each visit, the Dashboard will provide updated information focused on opportunities for optimizing GDMT.

Usual Care Arm

In the Usual Care Arm, eligible patients will be identified and sites will be alerted to the roster of patients eligible for study participation. These patients will be offered participation into a study of health status in those with chronic HFrEF and if agreeable they will be consented for inclusion to the study and information recorded. Data extracted may include the following: age, sex, LVEF, medication list (including doses), and laboratory results (such as basic metabolic panel). Following, the KCCQ-23 will be recorded via Medable, as above.

To maintain "usual care" as much as possible and avoid internal contamination bias, the managing site will not be aware the medical management is being monitored and the patient will not receive CardioSmart materials.

Follow up in the Usual Care arm will be at the discretion of the managing site. KCCQ-23 will be recorded remotely via Medable over the 6 months of follow up.

Analytics

At study completion, a data extractor (such as that provided by FIGmd) will extract the EHR data from storage and a data sheet across study visits will be provided to the analytic center at the Massachusetts General Hospital.

Safeguards

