- 8) Change in % eligible taking MRA during course of the study.
- 9) Change in % eligible taking SGLT2i during course of the study.
- 10) Relative improvement in GDMT composite score among subgroups of interest. This may include pre-specified analyses among patients the following characteristics:
 - a. Elderly patients (age ≥ 75 years)
 - b. New onset HF
 - c. Recently hospitalized patients
 - d. Those with LVEF <25%
 - e. Those with estimated glomerular filtration rate <30 mL/min/1.73m²
 - f. Baseline systolic blood pressure <100 mm/Hg
 - g. Absence of RASi at baseline
 - h. Absence of beta blocker at baseline
 - Patients with high baseline total medication burden (5 or more meds for all conditions)
 - j. Academic versus Private practice

Power calculations: The primary endpoint will compare central tendency in score changes between the two groups (6-month score - baseline score; this gives a range of score changes from -3 to +3). We will assume a 5% rate of score decreases, with rates for -3, -2 and -1 assumed equal between the two groups. To compare such changes a two-sided Wilcoxon ranksum test at a 0.05 significance level with 90% power will be employed. Assuming 5% of usual

care patients have an increase in score versus 10% of the intervention arm change by 1 point, a sample size of 2560 (1280 per arm) would be needed. Assuming a reasonable 20% loss to follow-up and/or missingness in this registry analysis, this makes a total of 3072 (1536 per arm). This not only provides power for the primary endpoint, but also for the secondary and exploratory endpoints, including change in QOL metrics.

12. Data and Safety Monitoring

This is an observational study comparing the effectiveness of two standards of care based on secondary use of data collected in the conduct of care and patient reported outcomes. The purpose of this study is not to gather data with regards to the safety profile and/or effectiveness of specific drugs. This study does not proscribe which treatment patients will receive. There is no Data Safety Monitoring Board for this study.

Adverse events (should they occur) will be captured at the clinical site level. Patients reporting adverse events will address these with their providing physician.

13. Data Storage and Confidentiality

Please refer to the Data Management section for details regarding how data captured in this study is stored and how the confidentiality of such data is maintained.

References

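### Sites of one health system may be randomised to different arms, and the safeguards against contamination do not cover a clinician who prescribes at sites in both

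*Protocol*

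**What the plan says.** **Unit of randomisation.** Protocol section 3 (Design and Procedures) states that "sites would be randomized into two arms: an intervention group and a usual care group". For practices outside the registry it adds that "non-PINNACLE sites within large health systems will be recruited and randomized into the intervention and usual care arms respectively". The Study Population list in the same section admits practices that belong to integrated health systems, both from the registry and from the other source. It admits stand-alone practices too.

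**Intervention.** It is delivered to the site: "the site will receive a pre-visit assessment of GDMT accompanied by recommended adjustment(s) using information extracted weekly", with distilled content of the ACC decision pathway in the dashboard. Patients also receive CardioSmart resources and app surveys.

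**Safeguards.** Section B (Data Management, Usual Care Arm) gives the aim and one means: to "avoid internal contamination bias, the managing site will not be aware the medical management is being monitored". Section 3 adds that, apart from quality-of-life collection, "study sites will not be contacted until the study has completed and they will be unaware of allocation to usual care", and that these sites receive no pre-visit guidance and are not specifically given the ACC tools. Usual-care patients receive no CardioSmart material (section B), and their consent material covers only the KCCQ-23 (section 6).

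**Before allocation.** Every invited site is told that "they might be asked to participate in an intensive intervention to improve GDMT prescription or in a study of QOL in HFrEF" (section 3).

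**The concern.** The primary endpoint is prescribing, and the intervention works largely through the prescriber. Section 2 suggests that limited understanding of, or confidence in, guideline targets may explain part of the treatment gap. Knowledge of that kind goes with the clinician from one clinic to another. If two sites of one system share a prescriber and fall in different arms, that prescriber sees dashboard recommendations at one site and treats usual-care patients at the other.

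Concealment would also be weaker there. All sites have been told of both possible roles, so a clinician who sees the dashboard at one site and only questionnaires at the other can infer the allocation.

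What is at stake is dilution: usual-care prescribing moves towards the intervention arm and the trial loses power for its primary comparison. This cannot be undone after allocation, and the choice of randomisation unit belongs in the protocol.

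**Working it through.** **1. What each safeguard reaches**

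- No pre-visit guidance and no ACC tools (section 3): limits what is sent to the usual-care site.
- No CardioSmart material (section B) and KCCQ-only consent material (section 6): limits what the usual-care patient receives.
- Site unaware of its allocation and of the monitoring (sections 3 and B): limits a change in behaviour caused by knowing the study's purpose.
- Randomisation by site (section 3): prevents mixing within a site.

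None of these covers a prescriber who works at sites in both arms. The protocol does not define a site by separate clinicians, and it does not require related sites to share an arm.

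**2. The plan's own sample size**

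Inputs from section 11: "two-sided Wilcoxon ranksum test at a 0.05 significance level with 90% power will be employed"; a 5% rate of decreases in both arms; increases in 5% (usual care) and 10% (intervention), read here as one point; 1280 per arm before loss. Decreases are spread equally over -1, -2 and -3.

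Probability that an intervention patient scores higher, counting ties as one half:

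P = 0.05 × 0.05 × 0.5 + 0.85 × (0.05 + 0.90 × 0.5) + 0.10 × (0.95 + 0.05 × 0.5) = 0.00125 + 0.425 + 0.0975 = 0.52375.

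Tie factor, from the average proportions of the two arms:

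T = 1 - [3 × (0.05/3)³ + 0.875³ + 0.075³] = 0.3296.

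Size per arm (Noether formula with tie correction):

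n = (1.960 + 1.282)² × T / [6 × (P - 0.5)²] = 10.507 × 0.3296 / (6 × 0.02375²) ≈ 1024.

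The plan states 1280, so its figure is not reproduced. At 1280 per arm these inputs give about 95% power (simulation: 0.955). That mismatch is a separate matter. It matters here only because it sets the starting point.

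**3. Effect of contamination**

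Let c be the share of all usual-care patients who respond exactly as intervention patients do. The documents give no value, so c is an assumption. The usual-care increase rate becomes 0.05 + 0.05c, which gives P - 0.5 = 0.02375 × (1 - c). T is recomputed each time.

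Power = Φ( (P - 0.5) / √(T/(6n)) - 1.960 ).

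| c | usual-care increase | P - 0.5 | T | power, n = 1280 | power, n = 1024 | n per arm for 90% |
|---|---|---|---|---|---|---|
| 0 | 5.0% | 0.02375 | 0.3296 | 95% | 90% | 1024 |
| 10% | 5.5% | 0.02138 | 0.3353 | 90% | 82% | about 1286 |
| 20% | 6.0% | 0.01900 | 0.3410 | 81% | 72% | about 1655 |
| 30% | 6.5% | 0.01663 | 0.3466 | 70% | 60% | about 2196 |

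The n = 1024 column shows the loss from a true 90% start.

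**4. Reading c**

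If a share f of usual-care patients is treated by cross-arm prescribers and they show a fraction r of the effect, then c = f × r. For example, f = 20% with r = 50% gives c = 10% and about 90% power at 1280 per arm. The 10%, 20% and 30% rows equal the exposed share only when r = 1. Clustering by site is ignored throughout.

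**The case against.** The strongest reply is that the risk may be small or absent.

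- **Staff sharing is not documented.** A reader might infer that shared clinicians do carry the intervention into usual care. The documents say only that sites lie within large systems. They do not say how many come from one system or whether any prescriber, nurse or pharmacist works at two of them. This stands, and it is why the point is stated as a risk.
- **There is more than one safeguard.** A reader might take the site's unawareness as the only protection. It is not: guidance, tools, patient materials and full study information are also withheld. This stands, although none of these reaches a shared prescriber.
- **Full spillover is unlikely.** The intervention includes a prompt for each patient before each visit and tools for the patient. A usual-care patient gets neither, and section 3's other barriers, such as the short visit, are not removed by remembered advice. This stands and makes full response an upper bound.
- **Exposure is limited.** Stand-alone practices are also recruited: "stand-alone, and other practice environments) with pre-existing data interfaces with study" partner is the condition for non-registry practices. Patients at practices with no cross-arm clinician are not exposed this way.
- **Patients seen at two sites.** A reader might conclude that they have no single arm. The documents largely answer this: consent is given at a site of one arm (section 5), and current or anticipated participation in a trial is an exclusion (section 3).
- **Direction.** Dilution works towards no difference. It threatens a missed effect and does not manufacture a false one.

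What remains is that the protocol states an aim to avoid contamination and has no rule for the route described here.

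**Conclusion.** The gap is real but modest. Allocation is by site, sites of one system may land in different arms, and nothing covers a clinician who prescribes in both.

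On the plan's inputs, with 1280 analysed per arm, full contamination of 10% still leaves about 90% power; 20% leaves about 81% and 30% about 70%. These figures rest on an assumed c, on full response in exposed patients, and on no allowance for clustering. They do not show that the trial is underpowered, because the documents give no basis for choosing a value of c. They do show that the plan's margin is used up at roughly 10%. The change is worth making before randomisation because it is cheap and cannot be made afterwards.

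**What to change.** In section 3, add a step before randomisation: ask each interested site whether it shares prescribing clinicians or heart-failure clinic staff with another interested site. Randomise sites that do as one unit, to the same arm.

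The cost is one rule and one question to sites. Where no staff are shared, nothing changes. The downside is somewhat fewer and less equal randomisation units, limited to sites that share prescribers. If links chain across several sites of a system, the merged unit could become large, so the answers should be reviewed before the list of units is closed. Randomising by whole health system would also close the gap, but would leave fewer and larger units than this rule needs.

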Site based procedures: Eligible patients will be enrolled utilizing software services provided by Medable. Medable hosts consumer-grade applications using their eCOA – including ePRO, eDiaries, eClinRo, eObsRo, and ePerfO – combined with eConsent, reminders & notifications, visit scheduling, and telemedicine on a single platform; their work will be essential in keeping track of patient reported outcomes and quality of life data.

Following enrollment, patients will be directed to Cardiosmart resources; such as those listed in Appendix A to use throughout their study experience—and after. As well, HRQoL will be assess at quarterly visits using the Medable app for completion of the KCCQ-23.

The Kansas City Cardiomyopathy Questionnaire (KCCQ) is a 23-item self-administered questionnaire developed to independently measure the patient's perception of their health status, which includes heart failure symptoms, impact on physical and social function, and how their heart failure impacts their quality of life (QOL) within a 2-week recall period.

The KCCQ tool quantifies the following six (6) distinct domains and two (2) summary scores:

KCCQ Symptom Domain: quantifies the frequency and burden of clinical symptoms in heart failure, including fatigue, shortness of breath, paroxysmal nocturnal dyspnea and patients' edema/swelling. An overall symptom score is generally used in analyses; subscale scores for both frequency and severity are also available.

KCCQ Physical Function Domain: measures the limitations patients experience, due to their heart failure symptoms, in performing routine activities. Activities are common, gender-neutral, and generalizable across cultures, while also capturing a range of exertional requirements.

KCCQ Quality of Life Domain: is designed to reflect patients' assessment of their quality of life, given the current status of their heart failure.

KCCQ Social Limitation Domain: quantifies the extent to which heart failure symptoms impair patients' ability to interact in a number of gender-neutral social activities.

KCCQ Self-efficacy Domain: quantifies patients' perceptions of how to prevent heart failure exacerbations and manage complications when they arise. This scale is not included in the summary scores.

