Adult patients ages 18 years and older with heart failure with Left Ventricle Ejection Fraction (LVEF) \leq 40% will be identified via an initial data extraction from interested sites. Participating sites will receive a roster of eligible patients, in order to best plan their enrollment. There will be no discrimination or bias with respect to patient inclusion on the basis of sex, race, or religion.

5. Subject Recruitment and Compensation

Upon identification of eligible patients, members of the clinical team will approach the patient with the offer to participate in a clinical study.

At **Intervention sites**, patients will be presented with the goals of the study, and given time to review the Informed Consent (prepared in their own language). Following, if the patient agrees, consent will be signed and patient included in the trial.

At **Usual Care sites**, patients will be presented with a proposal for periodic HFQoL assessment. If the patient agrees, consent will be signed and patient included in the trial.

No compensation will be offered to patients or families for participation in the registry or study.

6. Consent Process

Study consent will be provided electronically ("e-consent"), using Medable software. Consent materials will be provided with sufficient time for the patient to consider their participation in the study. For patients in the Intervention Arm of the study, consent materials will describe the study procedures, expected risks and expected benefits. For patients in the Usual Care arm, consent materials will only focus on the KCCQ-23. All consent materials will be in the patients' native language.

If the patient agrees to participation in the study, their informed consent will be recorded through e-consent processes with signature stored at Medable.

At any time, patients may withdraw consent. In such a circumstance, patients will be analyzed per intent to treat.

7. Subject's Capacity to Give Legally Effective Consent

Only those patients capable of giving informed consent will be enrolled in the study.

8. Study Interventions

In the Intervention arm, for each study visit, the site will receive a pre-visit assessment of GDMT accompanied by recommended adjustment(s) using information extracted weekly from the sites' EHR.

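### Intervention sites receive medication recommendations before the baseline visit, and the protocol does not place the baseline dose before that exposure, so the primary change score can be biased towards zero

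*Protocol*

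**What the plan says.** The order of events comes from several places in the protocol.

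- **Randomisation.** Section A.3 (Design and Procedures) says of interested sites that "sites would be randomized into two arms: an intervention group and a usual care group". Patients are approached afterwards.
- **Dashboard.** Section B, Intervention Arm, lists the steps in sequence. EHR data are extracted, weekly for the study. A dashboard is then built: "This dashboard will include a) lists of eligible patients for the study and b) an update on opportunities for further medication optimization". Next, "The dashboard containing the reveals will be conveyed to the sites". The step after that is enrolment: "Eligible patients will be enrolled utilizing software services provided by Medable".
- **Recommendations by visit.** Section 8 states: "In the Intervention arm, for each study visit, the site will receive a pre-visit assessment of GDMT", together with recommended adjustments. Section A.3 words this more widely, as before every patient appointment. Both sections name baseline, 3 months and 6 months as the visits.
- **Usual care.** These sites are told which patients are eligible. They get no pre-visit guidance and no patient materials.
- **Endpoint.** Section 11 defines the primary endpoint as the change in the composite from baseline to 6 months. Its power paragraph writes this as "6-month score - baseline score". The worked examples in that section speak only of an initial and a final dose.
- **Analysis file.** Section B, Analytics, describes a data sheet organised by study visit. No section says which extraction supplies the baseline medication list.

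**The concern.** A change score isolates the effect of an intervention only if the starting value is recorded before the intervention begins. Here the clinician at an intervention site holds a recommendation before the baseline visit and could act on it at that visit, or at an earlier routine appointment. With weekly extraction and a file indexed by visit, the list attached to the baseline visit could already show the new dose. That dose would then count as baseline rather than as change.

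Usual care has no comparable exposure before baseline, so the error would not cancel between arms. The first review of a patient's therapy may also be when most room for adjustment exists, so the response that is lost could be an important one.

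**Working it through.** **1. Is exposure before baseline stated?** For the baseline visit, yes. Recommendations go out ahead of each study visit (section 8), and baseline is a study visit (sections A.3 and 8). Exposure before enrolment is inferred from two things: the order of steps in section B, where the dashboard is conveyed and enrolment follows, and the wider wording on appointments in section A.3.

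**2. Effect on one patient.** Take the first example in section 11. The baseline ratio is 1/3 = 0.33, the final ratio is 3/3 = 1.0, and the change is 0.67. Suppose the beta-blocker criterion had already been met when baseline was recorded. The baseline ratio becomes 2/3 = 0.67 and the change 0.33. The final state is the same, but half the credited change is gone.

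**3. The plan's own power figure.** Inputs from section 11: two-sided Wilcoxon rank-sum test, alpha 0.05, power 90%; 5% decreases in each arm (taken here as 1.67% at each of -3, -2 and -1); increases of one point in 5% versus 10%; the rest unchanged.

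Let P = P(T > C) + 0.5 P(T = C), where T and C are the change scores in the two arms, and let K = 1 - sum of cubed pooled category proportions (tie correction). Then

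N = (1.960 + 1.282)² × K / [3 (P - 0.5)²]

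Power = Φ( √[3N (P - 0.5)² / K] - 1.960 )

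Moving a share e of patients from 0 to +1 gives P - 0.5 = e × (0.5 × 0.90 + 0.5 × 0.05) = 0.475e. For e = 0.05, P = 0.52375 and K = 0.3296, so N is about 2047 in total. The stated 2560 is not reproduced. At 2560 the power is 95.2%. That difference is a separate matter; the figures below start from 95.2%.

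**4. Size of the dilution.** The plan assumes that 5% improve without any intervention, so only the 5-point excess can shift because of the recommendations. Let f be the share of that excess that occurs before the recorded baseline. The documents give no value for f, so the rows are assumptions.

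| f | Intervention increase rate | Gap vs 5% | P | K | Power at 2560 |
|---|---|---|---|---|---|
| 0 | 10% | 5.0 | 0.5238 | 0.3296 | 95.2% |
| 10% | 5 + 5 × 0.90 = 9.5% | 4.5 | 0.5214 | 0.3239 | 90.8% |
| 25% | 5 + 5 × 0.75 = 8.75% | 3.75 | 0.5178 | 0.3153 | 79.4% |
| 1/3 | 5 + 5 × 2/3 = 8.33% | 3.33 | 0.5158 | 0.3104 | 70.2% |

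The calculation treats patients as independent. Because sites are randomised, true power would be lower in every row if outcomes correlate within sites.

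**The case against.** The strongest objection is that the choice of baseline record is normally fixed in the SAP, which is not at hand, and that the protocol names no wrong record. A pre-exposure list should also exist, because each recommendation is built from an extraction that came before it. The initial dose in the examples can fairly be read as the dose on entry. These points stand in part: if baseline is taken from such an extraction, the score is clean. They do not dispose of the issue, because the protocol itself sets the order of exposure and enrolment. A conventional SAP rule, such as the last record at or before consent, could still follow exposure.

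Three stronger readings are tempting, and the documents do not support them.

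- *Each patient's recommendations are released before consent.* The dashboard sentence gives no timing, does not say that its second item covers patients who have not consented, and as worded follows the non-PINNACLE data route. Release before consent is an inference from step order.
- *The trial will understate the effect.* This holds only if doses change before the baseline record. Staff who see titration opportunities while choosing whom to approach might also favour patients with room to improve, which would push the other way.
- *A modest early share removes most of the effect.* Applying f to the whole 10% increase rate would suggest that f = 25% halves the gap, since 10 × 0.75 - 5 = 2.5. That wrongly shifts the background 5% as well. Nor does having three scheduled visits establish f = 1/3, since section B also allows as-needed visits.

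**Conclusion.** The point holds as a conditional design weakness on the primary endpoint. Recommendations precede the baseline visit in one arm by the protocol's own wording, and apparently precede enrolment by its order of steps. Nothing in the protocol puts the baseline dose ahead of them. The treatment difference can therefore be biased towards zero.

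The size is unknown. At f = 10% the planned 90% power is just kept at 2560 analysed. At 25% to one third it is clearly lost. These figures rest on the plan's 5% and 10% rates, an equal split of decreases, no clustering, and an assumed f. It is worth settling before the first dashboard goes live, because later the choice depends on which records were kept.

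**What to change.** 1. Define the baseline score, in both arms, from an EHR extraction that predates the intervention. In the intervention arm this is the last extraction before that patient's recommendations are first released to the site. In usual care it is the last extraction before the site receives its roster. State that a record containing orders from the baseline visit is never used. The weekly schedule is described under the intervention arm, so confirm that a dated extraction is also kept for usual-care sites.
2. Optionally, show intervention sites only the eligibility roster until that baseline record is locked. Tying release to the lock, rather than to consent, avoids removing the promised pre-visit assessment when consent is taken at the baseline visit.
3. Section 4 says that patients "will be identified via an initial data extraction from interested sites". It does not say that this precedes randomisation. If that is confirmed, add a sensitivity analysis of change measured from it.

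The cost is a sentence or two in section 11, an optional display rule, and one analysis on stored data. The downside is small: for some patients the baseline record will be somewhat older than the consent date.
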